3.1 Scope of Study

This protocol describes the study activities that the ARDS, Pneumonia and Sepsis (APS) Consortium will complete together as a group, termed “Consortium-wide study procedures” and “Consortium-wide science.” The main body of this protocol is a *Master Protocol* and includes the overall rationale for the APS program, and the procedures for enrolling participants, collecting data, and collecting biospecimens.

Data and biospecimens collected using this master protocol will be used for three types of scientific studies:

- i. **APS Consortium-Wide Science:** Studies the APS Consortium investigators will complete and disseminate together using data and biospecimens collected under this master protocol. This science is described in the appendices of this protocol. Each of the 7 appendices describes one aim (study) of the APS Consortium-wide science. Consortium-wide science is funded by the NIH as part of the APS program.
- ii. **APS Clinical Center-Specific Studies:** Studies that individual Clinical Centers within the APS program will complete with data and biospecimens collected under this master protocol. The science of these studies will be completed without involvement of the full APS consortium and is not governed by this protocol. Use of data and biospecimens in Clinical Center-specific studies will be governed by other protocols, as necessary. Clinical Center-specific studies are funded by NIH as part of the APS program through grants to individual Clinical Centers.
- iii. **Ancillary Studies:** Studies that use banked data and biospecimens collected under this master protocol for conducting science not part of the APS Consortium-wide science nor the APS Clinical Center-specific studies. Use of data and biospecimens in ancillary studies will be governed by other protocols, as necessary. Ancillary studies are not funded as part of the APS program. Ancillary studies may be completed by APS Consortium investigators or investigators from outside the APS Consortium.

In summary, this protocol governs the collection of data and biospecimens for Consortium-wide study procedures and, in the appendices, describes the use of some of these data and biospecimens for consortium-wide scientific studies. Other studies, including Clinical Center-specific studies and Ancillary Studies, that will use data and biospecimens banked from this master protocol will be governed by other protocols managed by the investigators leading those studies.

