3.2 Protocol Documents

The APS Consortium study is governed by two study protocols:

- Protocol A (full protocol): This document is Protocol A. It describes all study procedures that a participant may complete during the course of the APS study and governs study procedures for participants who have completed informed consent for research participation. Protocol A contains two parts:
 - o Master protocol: Study procedures that govern enrollment, data collection, and biospecimen collection. The master protocol is described in the main text of this document.
 - o Consortium-wide science: specific analyses that will use data and biospecimens collected in this study and will be undertaken by the APS Consortium investigators collaboratively across the entire consortium. Consortium-wide science is described in appendices to this document.
- Protocol B (alteration protocol): This is a separate document not contained in the document presented herein. It describes a procedure for participation in the APS Consortium study with alteration of informed consent. Protocol B will be used for participants for whom informed consent for research cannot be obtained via the participant or a legally authorized representative prior to initiation of study procedures. Minimal risk procedures within the APS study may be completed using alteration of informed consent. Protocol B outlines the minimal risk procedures that may be completed with alteration of informed consent.

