8.2.2 Respiratory specimen collection during index hospitalization

During the index hospitalization, the following respiratory specimens will be collected: 1) nasal swabs to facilitate both microbiome profiling and pathogen detection, 2) oral swabs, 3) tracheal aspirate (TA) from patients receiving invasive mechanical ventilation, 4) heat moisture exchanger (HME) filter fluid from patients receiving invasive mechanical ventilation, 5) non-bronchoscopic bronchoalveolar lavage (NBBAL) fluid among a subset of patients receiving invasive mechanical ventilation.

Description of the NBBAL procedure in this study:

The NBBAL procedure will be completed in a subset of participants undergoing invasive mechanical ventilation after a safety screen for the procedure (see below) and consent is obtained. The NBBAL will be performed as soon as possible (and no later than 96 hours) after initiation of invasive mechanical ventilation. The NBBAL procedure will entail a catheter being inserted into the endotracheal tube and the catheter tip being wedged into a distal airway. Serial aliquots of sterile saline are instilled and aspirated with gentle suction (maximum volume instilled, 120ml). The aspirated fluid will be collected and processed as a biospecimen for the study.

Safety Screen for NBBAL in this study:

Participants meeting any of the following criteria will not undergo NBBAL for research purposes in this study:

1. Known pregnancy
2. $FiO_2 \geq 0.80$.
3. FiO_2 increased by > 0.1 in the prior hour.
4. $PEEP \geq 12$ cm H₂O.
5. $PEEP$ increased by > 2 cm H₂O in the prior hour.
6. Intracranial pressure > 15 or known labile intracranial pressure.
7. Open external ventricular drain (EVD).
8. Known pneumothorax.
9. Uncontrolled shock or rapidly escalating vasopressor requirements.
10. Unstable dysrhythmia.
11. Scheduled bronchoscopy.
12. Current therapeutic anticoagulation.
13. Known $INR > 2.0$.
14. Platelets $< 50,000$ /mcL.
15. Frank hemoptysis.
16. Partial lung resection or pneumonectomy.
17. Known pulmonary hypertension with pulmonary artery systolic pressure (PASP) > 55 cm H₂O.
18. Expected extubation attempt in the next 6 hours.
19. Clinical provider or site investigator judgement that procedure would not be safe.

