- b. The NBBAL time point is anchored on the time of completion of a research-dedicated NBBAL and may occur on any study day between Study Day 0 and Study Day 8. The NBBAL time point specimens should only be collected once and should be collected as soon as possible after intubation and the patient passes the NBBAL safety screen. Two specimen types are collected at the NBBAL time point: NBBAL fluid and CPT tubes (two 8 ml tubes). The window for collecting NBBAL fluid is between intubation and 96 hours later. Do not complete a NBBAL more than 96 hours after intubation. The CPT collection should occur as soon as possible after NBBAL fluid collection. For the NBBAL time point, only collect CPT tubes for patients who have NBBAL fluid collected. CPT collection for the NBBAL time point is in addition to the CPT tubes collected for other time points. The NBBAL time point may occur on the same study day as specimen collection for other time points. For example, if a patient has a NBBAL completed on Day 0, the specimens for both Day 0 and the NBBAL time point may be collected on Day 0, which would result in the collection of four 8ml CPT tubes on Study Day 0.
- c. Day 4 specimens are only collected from participants on invasive mechanical ventilation (IMV). Day 4 specimen collection is preferred on Study Day 4 or 5 but may be collected on Day 3 if Day 2 specimens were collected on Day 2 (instead of Day 3).
- d. The approach to blood volume collection is governed by 3 principles: collection of <50 mL combined on Day 0 and Day 2 to facilitate minimal risk blood collection volumes through day 2 in the alteration of informed consent protocol (Protocol B); collection of < 150 mL total blood volume during the index hospitalization; collection of <50 mL per timepoint at long-term outcome visits. The maximum blood volume listed in this table is the maximum volume any one participant will have taken. The volume of blood collected is variable among participants but will not exceed the volumes listed here.
- e. Participants who do not have blood collected for cellular analyses (CPT tubes) will have an additional 6 ml tube of EDTA collected at the study visit on Day 0, Day 6, and 3 months. Participants who do have blood collected for cellular analyses (CPT) will not have this extra tube of EDTA collected.
- f. During processing of CPT tubes, plasma will be saved and stored when possible.

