Tracheal aspirate fluid collection	Bleeding, localized pain, drop in oxygen levels (hypoxemia), and dislodgement of the tracheal tube. A drop in oxygen levels from tracheal aspirate collection is very unlikely to cause patient harm.	Only study or clinical personnel trained in the collection of tracheal aspirate fluid will collect this specimen. Tracheal suctioning is a routine clinical procedure and tracheal aspirates for this protocol will be done at times that tracheal aspirates are being collected as part of clinical care, whenever possible.
NBBAL procedure	Bleeding, localized pain, dislodgement of the tracheal	Only study or clinical personnel trained in the NBBAL procedure will complete this procedure for the study. NBBAL

Study procedure	Potential risks	Study methods to minimize risks
	tube, and drop in oxygen levels (hypoxemia), which if severe and uncorrected, can lead to organ injury and death. Serious injury from a NBBAL is rare (<1%). ²³	is a common clinical procedure in some hospitals. Only patients who are intubated will undergo the NBBAL procedure. Only patients who pass a pre-procedural safety screen under the supervision of the site investigator will undergo a NBBAL. Hypoxemia temporally related to a study NBBAL procedure will be collected as an AESI and reported to the sIRB and OSMB.
Long-term outcome surveys (via phone, SMS, or email)	No plausible physical risks. Participants might experience embarrassment or emotional discomfort.	Participants do not have to answer any questions that make them feel too uncomfortable. An on-call mental health specialist will be available to talk with patients that have severe emotional stress or suicidal thoughts.
Short physical performance battery (SPPB) [at in-person LTO visits]	SPPB assesses lower extremity functioning. It includes a balance test, a timed 4-meter walk test, and chair stand test. There is a small risk of falling. Activities may increase heart rate.	The testing will be performed by trained study staff. Movements are completed in a standard order, starting with easier movements. Participants will be able to skip any movement that they cannot do or feel would be unsafe to try.
CNS-Vital Signs [at in-person visits]	CNS vital signs is a computer based cognitive assessment. Participants might experience embarrassment or emotional discomfort from not being able to answer some questions.	Participants do not have to answer any questions that make them feel too uncomfortable.

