16.3.5 Aim 3 Study Procedures

HME filter fluid studies:

After passing a safety screen to rule out severe hypoxemia ($FiO_2 > 80\%$) or high PEEP (>15 cm H₂O), HME fluid will be collected on days 0, 2, 4, 6 and 14 if patient is mechanically ventilated by placing a fresh Airlife HME filter in the ventilator circuit for 4 hours. Patients who are intubated prior to enrollment will have the first (day 0) sample collected on the day of enrollment. The Airlife HME filter is optimal for these studies, with a small dead space volume and a reliable HME fluid yield of ~1-2 ml after a 4-hour dwell time.⁵ At study sites where heated ventilator circuits are routinely used, the heated circuit will be removed or turned off for the 4-hour HME dwell time. Once removed, HME filters will be centrifuged to collect exhaled breath condensate which will be frozen in small aliquots.

A panel of protein biomarkers representing key facets of lung pathology during acute respiratory failure will be measured in duplicate in HME samples including IL-6, IL-8, TNFR1, MCP1, RAGE, SP-D, Angiopoietin-2, ICAM-1, procollagen peptide-3, protein C, PAI-1 and total protein.

NBBAL studies:

All patients that are initiated on mechanical ventilation will be considered for NBBAL. Ideally, NBBAL will be performed within 24 hours of initiation of mechanical ventilation. However, we recognize that this might not be feasible for all participants. Therefore, NBBAL may be performed as late as 96-hours after initiation of mechanical ventilation. Safety criteria for NBBAL include $FiO_2 \leq 75\%$, $PEEP < 15$, $INR \leq 3.0$, and platelets $> 50,000 / \text{ul}$. All must be met at the time of the procedure. Prior to performing NBBAL, the patient is placed on 100% FiO_2 for 10 minutes. BAL is performed using a flexible 16 gauge catheter that is gently advanced through the endotracheal tube to “wedge” the distal tip of the catheter. Serial aliquots of saline are instilled into the catheter and then aspirated. The maximum instillation volume is 120 ml.

Aspirated BAL fluid will be pooled and placed in a sterile collection container and kept on ice until processing. BAL fluid will be run through a 70 micron strainer to remove mucus and debris. Fluid will be centrifuged to pellet cells. Cell-free fluid is gently aspirated and aliquoted for banking. Cells will be washed once, and then preserved for RNA sequencing studies.

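### Section 16.3.5 states NBBAL safety limits that conflict with the Section 8.2.2 screen: looser for PEEP and INR, stricter for FiO2 and for platelets of exactly 50,000

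*Protocol*

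**What the plan says.** Section 8.2.2 (master protocol) lists 19 criteria under its NBBAL safety screen, introduced by "Participants meeting any of the following criteria will not undergo NBBAL for research purposes in this study". Four are numeric limits that recur in the appendix: FiO2 ≥0.80 (item 2), PEEP ≥12 cm H2O (item 4), known INR >2.0 (item 13) and platelets <50,000/mcL (item 14).

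Section 16.3.5 (Appendix C, Aim 3) returns to the procedure under its NBBAL studies heading. The sentence beginning "Safety criteria for NBBAL include" gives FiO2 ≤75%, PEEP <15, INR ≤3.0 and platelets >50,000/ul, followed by "All must be met at the time of the procedure". The same paragraph gives operating detail: ten minutes on 100% oxygen beforehand, then "BAL is performed using a flexible 16 gauge catheter that is gently advanced through the endotracheal tube".

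On which part governs, Section 3.2 describes the master protocol as "Study procedures that govern enrollment, data collection, and biospecimen collection". Section 3.1 says that the protocol, "in the appendices, describes the use of some of these data and biospecimens for consortium-wide scientific studies".

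Elsewhere the protocol speaks of one screen. Table 7 footnote b (Section 10) says that the NBBAL time point specimens "should be collected as soon as possible after intubation and the patient passes the NBBAL safety screen". Table 13 (Section 13.1) lists the screen as a risk control: "Only patients who pass a pre-procedural safety screen under the supervision of the site investigator will undergo a NBBAL".

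**The concern.** A safety screen should give one answer for a given patient. Here a patient at PEEP 13 or INR 2.5 is barred by Section 8.2.2 and meets the corresponding limit in Section 16.3.5. A patient at FiO2 0.78 passes the Section 8.2.2 limit and fails the one in Section 16.3.5.

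The limits bear on the risks that the protocol itself names. Table 13 lists bleeding and hypoxemia among the NBBAL risks, and says that severe uncorrected hypoxemia can lead to organ injury and death. Hypoxemia after NBBAL is the only adverse event of special interest in Section 14.2.2. FiO2 and PEEP limits address that hazard, and INR and platelet limits address bleeding.

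Section 16.3.5 is not background text. It is written as an operating description and is the only place that gives the pre-oxygenation step and the catheter gauge. A team that consults it for those details meets a short list of limits with no pointer to Section 8.2.2, and could apply its looser PEEP and INR limits.

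**Working it through.** No sample size, power or error-rate figure is involved. The check sets the two lists side by side.

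**Same procedure?** Yes. Both sections describe a catheter wedged through the endotracheal tube, serial saline aliquots, a maximum of 120 ml instilled, and a limit of 96 hours after the start of mechanical ventilation.

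**Permitted ranges.** Section 8.2.2 states exclusions, so each is inverted to give what it allows. Section 16.3.5 gives no unit for PEEP; cm H2O is assumed.

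| Parameter | Allowed by 8.2.2 | Allowed by 16.3.5 | Disputed range | Appendix is |
|---|---|---|---|---|
| FiO2 | <0.80 | ≤0.75 | >0.75 to <0.80 (width 0.80 − 0.75 = 0.05) | stricter |
| PEEP, cm H2O | <12 | <15 | 12 to <15 (width 15 − 12 = 3) | looser |
| INR | ≤2.0 | ≤3.0 | >2.0 to 3.0 (width 3.0 − 2.0 = 1.0) | looser |
| Platelets | ≥50,000 | >50,000 | exactly 50,000 | stricter |

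**Boundary cases**, with all other values normal:

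| Case | 8.2.2 | 16.3.5 |
|---|---|---|
| PEEP 12 | fail | pass |
| PEEP 14 | fail | pass |
| INR 2.1 | fail | pass |
| INR 3.0 | fail | pass |
| FiO2 0.76 | pass | fail |
| FiO2 0.79 | pass | fail |
| Platelets 50,000 | pass | fail |

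The two lists disagree in all seven cases, and in both directions. Neither is simply a tighter version of the other.

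**Coverage.** Items 2, 4, 13 and 14 of Section 8.2.2 have a counterpart in Section 16.3.5. The other 19 − 4 = 15 do not. The appendix list is worded as non-exhaustive, so the missing items are not a contradiction. That wording does not explain different cut-offs for the four items it does give.

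**Does any reading reconcile them?**

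- *Section 8.2.2 alone governs.* All four appendix limits are then wrong.
- *Both apply together.* The joint rule is FiO2 ≤0.75, PEEP <12, INR ≤2.0 and platelets >50,000. The appendix PEEP and INR limits then have no effect, the Section 8.2.2 FiO2 limit is too loose, and its platelet limit is too loose at 50,000. The protocol nowhere states this joint rule.
- *Section 16.3.5 alone governs.* This contradicts the absolute bar in Section 8.2.2.

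No reading leaves both lists correct.

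**The case against.** The strongest reply is that the document largely settles precedence. Section 3.2 gives biospecimen collection to the master protocol, and Section 3.1 says the appendices describe use. Section 8.2.2 is an absolute bar, and its list carries the safety-screen title that the schedule of events uses. The appendix limits read as necessary conditions, not sufficient ones, so meeting them lifts no exclusion in Section 8.2.2. Read correctly, the looser PEEP and INR limits authorise no lavage. Item 19 of Section 8.2.2 also lets the clinician or site investigator stop the procedure on judgement, and only trained personnel perform it.

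Most of this stands: Section 8.2.2 probably controls, and the extra safeguards reduce the consequence. It does not remove the conflict. There is no explicit precedence clause, and Section 16.3.5 goes beyond use to describe how the specimen is collected. Even with Section 8.2.2 in control, a lavage at FiO2 0.78 satisfies the governing screen and breaches the requirement in Section 16.3.5 that all its limits be met.

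Some elements carry little weight. The platelet difference is a single boundary value. The FiO2 interval matters only where settings between 0.75 and 0.80 are used; a site that moves FiO2 in steps of 0.05 has none. The documents do not say why the appendix limits differ, so they may be deliberate or left over from other text.

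**Conclusion.** The inconsistency is real and is in current protocol text. All four shared numeric limits for research NBBAL differ between Sections 8.2.2 and 16.3.5, two in each direction. The disputed ranges are 3 cm H2O of PEEP, 1.0 of INR, 0.05 of FiO2 and a single platelet value. PEEP and INR matter most for safety, because there the appendix is the more permissive.

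About 700 participants are expected to have NBBAL (Table 9, Section 16.3.8). The number in the disputed ranges cannot be computed, because the protocol gives no distribution of FiO2, PEEP, INR or platelets. No analysis or sample size changes. What is at stake is inconsistent application of a safety screen across sites. The point should be fixed, and confidence in it is high. The conclusion rests only on the printed limits and on the two sections describing the same procedure, which the shared volume and time limits support.

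**What to change.** 1. Have the investigators confirm the intended FiO2 limit (<0.80 or ≤0.75) and whether a platelet count of exactly 50,000 passes. If either answer differs from Section 8.2.2, amend it there.
2. Delete the four numeric NBBAL limits from Section 16.3.5 and refer the reader to the Section 8.2.2 screen. The pre-oxygenation and catheter details can stay.
3. Notify sites of the single operative list.

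The cost is a one-line amendment to Section 16.3.5, a boundary change in Section 8.2.2 only if step 1 requires it, and a site memo. No new data or patients are needed.

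The same amendment could tidy a related point that is not a contradiction. Section 16.3.5 also sets a screen for HME filter collection (FiO2 >80% or PEEP >15 cm H2O) that neither Section 8.2.2 nor Table 7 mentions. It could be carried into one of them.

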16.3.6 Aim 3 Data, Images, and Biospecimens Used from the APS Consortium

To identify acute lung-specific APS phenotypes and endotypes using airspace biospecimens (Objective 1) we will utilize clinical data, chest radiograph images and HME fluid that are collected for the APS study. To determine relationships between acute lung-specific APS phenotypes and short- and long-term pulmonary dysfunction (Objective 2) we will utilize clinical data including duration of mechanical ventilation and mortality from APS and long-term outcome data including pulmonary function testing (spirometry, DLCO) and CT fibrosis scoring that will be obtained in approximately 500 survivors at 12 months. In addition, we will utilize plasma biomarker levels and LCA phenotyping results that are planned for the entire APS cohort for comparison to lung-specific phenotypes derived from respiratory variables and biomarkers measured in HME fluid (Objective 3).

16.3.7 Aim 3 Statistical Analysis

As with all aims, the final statistical analysis plan will be fixed and filed prior to conducting the analysis. Here, we describe one potential approach for this aim, which will either be confirmed and fleshed out or updated with new methods available at the time of analysis. The primary analysis will include all enrollees to determine if there are latent respiratory phenotypes that are common to all critically ill patients; mechanically ventilated patients enrolled in the APS study will include patients intubated for pneumonia, sepsis, ARDS, and other causes of acute respiratory failure. Secondary analyses will focus within subgroups of patients who have been clinically phenotyped as having sepsis (both pulmonary and non-pulmonary), ARDS, and pneumonia. Some patients will be classified into more than one subgroup.

To approach this aim, a *de novo* latent class analysis (LCA) using previously described methods might be proposed.² For the primary analysis, clinical and respiratory variables along with HME biomarkers measured on the first day of mechanical ventilation would be considered. These variables include protein biomarkers (IL-6, IL-8, TNFR1, MCP1, RAGE, SP-D, Angiopoietin-2, ICAM-1, procollagen peptide-3, protein C, PAI-1 and total protein) along with age, sex, etiology of acute respiratory failure, PaO₂/FiO₂, PEEP, static compliance of the respiratory system, ventilatory ratio,¹⁰ and RALE score.¹¹ Respiratory and HME biomarker data available at a later timepoints for patients who are still intubated may be included in the analysis to determine whether phenotypes identified at the onset of ARF are stable over time and whether new respiratory phenotypes emerge in those who remain in ARF. Once we have determined whether latent respiratory phenotypes are present, we will investigate phenotype generalizability and stability, and test associations between respiratory phenotypes and pre-illness factors such as air pollutant exposure and socioeconomic factors.

For long-term outcomes, we will focus first on two key hypotheses. First, we hypothesize that acute lung epithelial injury as measured by HME fluid RAGE and SP-D will be associated with development of fibrotic lung changes (increased lung fibrosis scoring on CT, decreased FVC). Second, we hypothesize that the severity of lung endothelial injury as measured by HME fluid Ang-2 and ICAM-1 will be associated with long-term destruction of the lung vascular bed as measured by DLCO. The dependent variables of interest are continuous variables and will be DLCO, FVC, lung fibrosis score. Independent variables include age, sex, HME biomarker data from both day 1 and latest day available, ventilator settings, RALE score, duration of mechanical ventilation, underlying cause of ARF (pneumonia, ARDS, sepsis, other). The initial proposal is for use of linear regression models; dependent variables may be log-transformed to improve fit. Analyses done are expected to include the entire cohort, as well as in subgroups divided by clinical syndrome (pneumonia, ARDS, sepsis). To determine whether long term respiratory outcomes differ by any *de novo* respiratory phenotypes, we can include the phenotype variable and its interaction terms with the main independent variables of interest.

We plan to check for concordance and discordance between novel respiratory phenotypes identified in this Aim and previously derived phenotypes based on clinical and biomarker data and the LCA approach. We will then assess reasons for concordance and discordance. If the same number of clusters are identified with each analysis, standard metrics including Cohen's Kappa will be used to assess the degree of concordance. Identifying a different number of clusters for systemic vs. respiratory phenotypes, or the same number with lack of concordance, may indicate that respiratory phenotypes differ from systemic inflammatory phenotypes. When different numbers of clusters are identified between aims, correlation between cluster variables will be assessed, as well as evaluating whether some clusters function as sub-clusters of those identified in other aims.

Finally, a key question is whether the biologic mechanisms that form the basis for NBBAL endotypes are reflected in the blood. This can be achieved by exploring targeted gene expression profiles and weighted gene cluster network analysis (WGCNA) in bulk RNA seq between peripheral blood PBMCs and NBBAL.

